6.1.2. Analysis of Covariance Model for Change from Baseline Endpoints

The analysis of covariance (ANCOVA) models of change from baseline to Week 26 efficacy endpoints will include treatment group, strata (that is, baseline HbA1c category, baseline BMI category, and metformin use [yes, no]) as fixed effects and baseline measurement as a covariate. If the analysis is for the primary endpoint, baseline HbA1c category will not be included in the model in addition to the continuous covariate of baseline HbA1c.

The ANCOVA will present LS mean estimates and 2-sided 95% CIs for mean changes from baseline within and (when warranted) between treatments. T-statistics corresponding to the Type III sums of squares for the differences in the LS means will be used to obtain p-values for treatment group comparisons.

6.2. Patient Disposition

The primary reasons for discontinuation by treatment will be listed and summarized. Using the Fisher's exact test, the percentage of patients discontinuing from each treatment will be compared.

Patient statuses at the end of the 26-week treatment period displaying the numbers of patients will be summarized:

- entered
- screen failed, along with the primary reason for screen failure
- randomized
- randomized and not treated
- permanently discontinued from treatment
- discontinued from study, along with the primary reason for study discontinuation
- completed 26 weeks blinded treatment
- completed study.

The summary of status at the end of the 26-week treatment period will count patients by randomized treatment group and overall, except that "Entered" and "Screen failures" only apply to the overall entered population. Entered is defined as signing an ICF. The percentage of patients discontinuing from each treatment using the Fisher's exact test will be provided.

6.3. Analysis Populations

Five patient populations for the analyses with detailed information are defined in Table 6.1. Unless otherwise specified, listings will include all randomized patients.

Table 6.1. Analysis Populations

Population	Definition		
All Entered	All patients who signed informed consent forms (ICFs)		
Intend-to-Treat (ITT)	All patients who were randomized to a treatment arm		
Safety Population	All patients who took at least 1 dose of double-blind treatment. The taking of at least		
	1 dose will be established using the "Study Treatment" electronic case report form (eCRF)		
	pages. In all safety analyses, patients by the actual treatment group will be presented.		
Modified Intent-to-	All randomized patients who have taken at least 1 dose of the study medication and have		
Treat (mITT)	at least 1 post baseline measurement. Analyses, by planned treatment group, using the		
	mITT population will be presented.		
Per-Protocol (PP)	All patients in mITT who complete the study and also meet the following criteria:		
	Have been appropriately randomized		
	Have not discontinued from the study for any of the early discontinuation criteria		
	Have not missed 4 or more doses during the treatment period		
	Have not been rescued or taken a concomitant antihyperglycemic medication besides		
	metformin for >7 cumulative days during the treatment period		
	No important protocol deviations. The deviations to be used for excluding patients		
	from the PP population will be specified prior to study unblinding.		

6.4. Patient Characteristics and Medical History

Demographic and baseline characteristics, by treatment and overall, will be summarized using the mITT population and PP population. Categorical variables will be summarized using frequencies and percentages, and compared between treatments using a Pearson Chi-Square test. Continuous variables will be summarized using means and SDs, and compared between treatments using a 1-way analysis of variance.

Demographic and baseline diabetes characteristics in listings for each patient randomized will be provided.

The numbers and percent of patients with general medical history findings will be provided using the randomized (that is, ITT) population. A listing by patient will be provided.

6.5. Treatment Compliance

Treatment compliance will be listed using all randomized patients and summarized using the mITT population. For a given patient, overall compliance for treatment period is defined as not missing 2 or more consecutive doses of the assigned treatment or missing 4 or more doses at any point through the entire study. Patients who miss 4 or more doses at any point during the study will be considered significantly noncompliant, will not be included in the PP analysis.

Safety population during the 26-week treatment period by treatment group will be used to summarize the number and percent of patients compliant at 26-week.

6.6. Exposure of Study Treatment

For the safety population, exposure for each patient during the treatment period of the study, will be calculated and will be summarized by treatment group.

The extent of exposure to study medication (LY3298176, placebo, or dulaglutide) during the 26-week treatment period is defined as:

Date of last dose of study medication +7 days - date of first dose of study medication.

The extent of exposure to study medication will be summarized at 26 weeks using the safety population and categorized by the actual treatment group. The number and percent of patients with an extent of exposure within pre-specified day ranges for the 26-week treatment period will be summarized by treatment group.

The mean, SD, median, minimum, and maximum days of exposure will also be presented.

In addition, the exposure in terms of total patient-years will be calculated by treatment group, using the sum of the exposure to study medication of all patients (in years) in a treatment group.

A patient listing of study medication taken will also be generated.

6.7. Concomitant Drugs

Listings and summary of concomitant therapies by treatment group will be provided.

Previous and concomitant medications will be summarized using the randomized (that is, ITT) population by drug class with generic drug name and planned treatment group, as defined by the World Health Organization (WHO) drug dictionary most current at the time of DBL. A summary will be produced for all concomitant medications during the:

- 26-week treatment period
- follow up period

All previous and concomitant medication use will be listed.

Previous medication is defined as medication with a recorded stop date before the date of the first dose of study treatment.

Concomitant medication during the 26-week treatment period is defined as medication with either a recorded medication start date falling:

- within the 26-week treatment period, or
- prior to the first day of study medication but continuing or stopping after at least 1 day on study medication.

This means that concomitant medications for the 26-week treatment period will be any medication taken for at least 1 day during the 26-week treatment period.

Similarly, concomitant medications for the follow-up period will be any medication taken for at least 1 day during the follow-up period.

Anti-hyperglycemic medication taken for any reason as well as taken as rescue for severe, persistent hyperglycemia will be summarized and listed. Metformin dose at baseline will be summarized, as will proportion of patients who adjusted their metformin dose during the trial.

6.8. Protocol Deviations

Important protocol deviations will be listed for all randomized patients and summarized by treatment group. A list of important protocol deviation criteria for patients from the trial issues management plan is given in Appendix 3. Patients who deviate from the protocol in ways that would possibly affect efficacy results are going to be excluded from the per protocol analyses. That information can be found in Appendix 3. Patients meeting criteria for important protocol deviations will be identified either by statistical programming or based off of study monitoring that maintained by the study clinical trial manager (CTM). The final list of important protocol deviations will be reviewed and documented in the Important Protocol Deviations document by the study team prior to the primary outcome DBL.

6.9. Efficacy Analyses

The primary efficacy analysis, which is the Bayesian dose-response analysis on the change in HbA1c, will be performed on mITT population without rescue (i.e., data after use of rescue medication will not be included). Unless specified, all other efficacy analyses will be performed on mITT population on treatment without rescue (i.e., data after rescue medication or data after study treatment discontinuation will not be included). Some key efficacy measures, such as HbA1C and body weight, will also be analyzed on mITT population with all available data and on a PP dataset.

With the exception of the dose-response analyses on the HbA1c and body weight endpoints, all statistical models will include all treatment groups, including LY3298176, placebo, and dulaglutide.

6.9.1. Primary Outcome and Methodology

The primary efficacy outcome is HbA1c change from baseline to the 26-week endpoint.

6.9.1.1. Primary Analyses

The primary objective is to examine the probability each LY3298176 dose has demonstrated superiority relative to placebo using a superiority margin of –0.8%. Analyses will also consist of the 90% one-sided credible interval for the difference in mean response for each LY3298176 dose versus placebo at 26 weeks.

The primary analyses will be performed on the mITT without rescue analysis set using a Bayesian dose-response model and will include data from the blinded 26-week treatment period. The model will include LY3298176 doses, dulaglutide, and placebo.

The Hierarchical Logistic Model will be used to model the dose response in HbA1c change from baseline to the 26-week endpoint, . . The placebo group (d=0) will be modeled with the LY3298176 doses (d=1,...,D-1) using the Hierarchical Logistic model. Dulaglutide(d=D) is modeled independently. Each dose arm follows a prior structure as specified below:

$$\begin{cases} \theta_{dT} \sim a_1 + \frac{a_2 x_{dT}}{x_{dT} + a_3} + \varsigma_{dT}, & d = 0, ..., D - 1 \\ y_T | a_1, a_2, a_3, \varsigma_{dT}, x_{dT} \sim N(\theta_{dT}, \sigma^2), \\ \theta_{dT} \sim N(\mu_{dT}, \nu_{dT}^2) = N(0, 30), & d = D \end{cases}$$

where

$$\begin{cases} \varsigma_{dT} \sim N(0, \alpha_4^2), & \sum \varsigma_{dT} = 0 \\ \alpha_4^2 \sim IG\left(\frac{\Lambda_n}{2}, \frac{\Lambda_\mu^2 \Lambda_n}{2}\right), \\ a_i \sim N(\Lambda_i, \lambda_i), & \text{for } i = 1, 2 \\ a_i \sim N^+(\Lambda_i, \lambda_i), & \text{for } i = 3 \\ \sigma^2 \sim IG\left(\frac{\sigma_n}{2}, \frac{\sigma_\mu^2 \sigma_n}{2}\right), \end{cases}$$

and $\Lambda_1 = 0$, $\Lambda_2 = 0$, $\Lambda_3 = 20$, $\Lambda_{\mu} = 3$, $\Lambda_n = 1$, $\sigma_{\mu} = 3.3$, $\sigma_n = 1$, and $\lambda_i = 30$, where i = 301,2,3. T denotes the final time point at 26 weeks. The parameters a_1 , a_2 , and a_3 represent, respectively, the basal effect when the dose level is zero, the maximum effect that can be achieved by any dose level, and the dose level that produces half of the maximum improvement (ED₅₀). So $a_2 - a_1$ gives the maximum improvement attributable to the drug. The parameter ς_{dT} is equivalent to a dose-specific random effect term but the sum of ς_d is constrained at zero to make sure it is identifiable from the error term, σ^2 .

For placebo (d=0) and LY3298176 (d = 1,...,D-1), each successive θ_{dT} is modeled using all other estimated dose level means.

Additional definitions are as follows:

- d is the dose arm index, with d = 0,...,D (d=0 as placebo, and d=D as dulaglutide)
- D is the number of non-placebo dose arms, including dulaglutide. D is also the dose arm index for dulaglutide.
- x_{dT} is the dose strength, with d = 0, 1, ..., D-1 in ascending order. Dulaglutide is not included in the Hierarchical Logistic model, and therefore does not require a dose strength.
- Λ_i and λ_i are, respectively, the prior means and variances of a_i , i = 1,2,3.
- θ_{dT} is the modeled dose arm effect at dose d at the final time point T of the 26-week of the study.
- E (1/a₄) = 1/Λ_μ and Λ_n represents the weight of the prior information carried in Λ_μ.
 E (1/σ²) = 1/σ_μ and σ_n represents the weight of prior information carried in σ_μ².

The dose strength, x_{dT} , used in the model will reflect the actual selected doses for the study. The planned values for x_{dT} are shown in Table 6.2. Dulaglutide is modeled separately. The magnitude of the parameters x_{dT} impact the estimation in the dose-response model.

Dose Strength Parameter	Dose Strength (mg)
x_0	0*
x_1	1
x_2	5
x_3	10
x_4	15
x_5	NA

Table 6.2. Dose Strength Parameters and Corresponding Dose Strengths

Abbreviation: NA = not applicable.

Any missing responses for the primary outcome will be imputed using the longitudinal integrated two-component prediction (ITP) model. This is a slight deviation from the protocol, which is specified to use the Simple Linear Regression (SLR) model. The model is as follows:

$$Y_{djt} = (\omega_d + S_{dj} + \varepsilon_{djt}) \times (\frac{1 - e^{k_d t}}{1 - e^{k_d \times 26}}) = f(d, t) + (S_{dj} + \varepsilon_{djt}) \times (\frac{1 - e^{k_d t}}{1 - e^{k_d \times 26}})$$

Where Y_{djt} represents the response for dose d, subject j at time t. where time is t = 1, 2, ..., 9 (1, 2, 4, 8, 12, 16, 20, 24, 26 weeks), T is the 26 week time point, patient is $i = 1, ..., N_d$, where N_d is the number of patients for dose d, and d = 0, ..., D. f(d,t) represents the mean response.

The prior distributions for time t and d = 0, ..., D dose levels are as follows:

$$\begin{cases} \omega_{d} \sim N(\omega_{\mu}, \omega_{\sigma}^{2}) = N(0,3^{2}), \\ S_{dj} \sim N(0, \tau^{2}), \\ \varepsilon_{djt} \sim N(0, \lambda^{2}), \\ \lambda^{2} \sim IG\left(\frac{\lambda_{n}}{2}, \frac{\lambda_{\mu}^{2} \lambda_{n}}{2}\right), \\ \tau^{2} \sim IG\left(\frac{\tau_{n}}{2}, \frac{\tau_{\mu}^{2} \tau_{n}}{2}\right), \\ k \sim N(\mu_{k}, \sigma_{k}^{2}), \end{cases}$$

where $\lambda_{\mu}=1$ and $\lambda_{n}=1$, $\tau_{\mu}=1$ and $\tau_{n}=1$ and $IG(x|\alpha,\beta)$ is an inverse gamma distribution $\frac{\beta^{\alpha}e^{-\beta/x}}{x^{\alpha+1}\Gamma(\alpha)}$, μ_{k} =-0.1, and σ_{k} =1.

Since there are two treatment arms have titration doses, we will implement a titration ITP model for those two arms if data permits. Specifically, the mean response will be modeled as

$$f_{d,t_c}(t) = f(t;d_1) + \sum_{i=1}^{m-1} (f(t-t_{ci};d_{i+1}) - f(t-t_{ci};d_i))I(t > t_{ci}),$$

where $d = (d_1, d_2, ..., d_m)$ are the doses a subject takes, and $t_c = (t_{c1}, t_{c2}, ..., t_{c,m-1})$ are the times of the dose change.

^{*} Different FACTS files are used when comparing to placebo and dulaglutide. When comparing to dulaglutide, $x_0 = 1$ because of limitations in FACTS.

The longitudinal ITP and Hierarchical Logistic dose-response models will be analyzed using Markov Chain Monte Carlo (MCMC). To obtain final results, at least 60 000 total MCMC iterations will be run, with at least 10 000 initial MCMC iterations being discarded as burn-in and at least 50 000 iterations used in calculations. Each iteration of the MCMC chain progresses as follows: Missing observations for the 26-week time point T are imputed for each subject at each dose level "d" using the longitudinal ITP model. These data are then used in the Hierarchical Logistic dose-response model to update θ_{dT} . Therefore, at each MCMC iteration, parameters from both the ITP model as well as the Hierarchical Logistic model will be updated. The 2 models are linked together through the missing data by imputing the missing response at the 26-week endpoint. If there was no missing data, the longitudinal model would not affect the fit of the Hierarchical Logistic model.

Primary analysis will consist of the posterior mean and 90% one-sided credible interval for the difference in mean response for each LY3298176 dose versus placebo (posterior mean and 90% credible intervals for $\theta_{dT} - \theta_{0T}$ for d = 1, ..., D-1 at the 26-week T time point). The primary objective will be met if at least 1 of the 90% credible intervals excludes -0.8% HbA1c at 26 weeks in favor of LY3298176. No adjustment for multiplicity will be performed.

Probabilities based on posterior distributions of each dose group's mean response exceeding the placebo group's mean response by clinical thresholds of interest (by -0.3%, -0.6%, and -1.2%) will be provided.

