6.9.1.2. Secondary Analysis of the Primary Efficacy Outcome

This secondary analysis is to evaluate the non-inferiority of LY3298176 to dulaglutide for the change in HbA1c from baseline to 26 weeks, using the primary analysis model. This secondary objective will be met if the upper limit for the 90% credible interval for the difference between LY3298176 and dulaglutide less than 0.3% (non-inferiority margin) for at least one LY3298176 dose arm.

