6.9.1.3. Supporting Analyses of Primary Outcome

The following supportive analyses will be performed for the primary outcome:

- An analysis using the same statistical model as the primary analysis will also be performed using mITT population on treatment without rescue dataset.
- The change in HbA1c from baseline will be analyzed using MMRM with restricted maximum likelihood estimation described in section 6.1.1. Comparisons between each LY3298176 dose arm with dulaglutide and placebo will be made. This analysis will be performed on three analyses sets: mITT population on treatment without rescue data, mITT population with all data, and PP dataset.
- An ANCOVA model will be used on the last observation carried forward (LOCF) endpoint of HbA1c as described in section 6.1.2. using MITT on treatment without rescue, and mITT population.

Table 6.3 describes the analyses to meet the primary objective, all performed on the HbA1c change from baseline values, including the above sensitivity analyses.

Analysis Type	LOCF or Observed Values	Analysis Set
Hierarchical Logistica	Observed	mITT without
		rescue
Hierarchical Logistic	Observed	mITT on treatment
		without rescue
MMRM	Observed	mITT
MMRM	Observed	PP
MMRM	Observed	mITT on treatment
		without rescue
MMRM, subgroup analyses	Observed	mITT on treatment
		without rescue
ANCOVA	LOCF	mITT on treatment
		without rescue,
		mITT

Table 6.3. Summary of Analyses for Primary Outcome

Abbreviations: ANCOVA = analysis of covariance; HbA1c = hemoglobin A1c; LOCF = last observation carried forward; mITT = modified intent-to-treat; MMRM = mixed model repeated measures; PP = per protocol.

a primary analysis

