6.9.2. Efficacy - Secondary Outcomes

6.9.2.1. Dose Response Analyses on HbA1c and Body Weight

Change from baseline in HbA1c at 12 weeks will be accessed using a superiority margin of - 0.8% to placebo as well as a non-inferiority margin of 0.3% to dulaglutide, based on the primary analysis model.

The body weight change from baseline at both 12 and 26 weeks will compare to a superiority margin of -2 kg to placebo. Similar Bayesian dose-response analysis as for HbA1c will also be performed for the change in body weight, except with an exponential dose-response model:

$$\begin{aligned} \theta_{dT}{\sim}a + b*d^{\gamma} + \varsigma_{dT}, & d = 0, ..., D-1 \\ y_{T}{\sim}N(\theta_{dT}, \sigma^{2}), & \end{aligned}$$

 γ is a sigmoidicity parameter indicating shape or steepness of dose response. The priors for each parameters are: $\alpha \sim N(0, 50)$, $b \sim N(1, 10)$, $\gamma \sim N(1, 5)$. Other dose-response models may be explored if the exponential dose-response model does not fit the data well. The analysis will be performed in two datasets: mITT without rescue, and mITT on treatment without rescue.

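### The primary Bayesian model ignores baseline HbA1c, metformin use and BMI category, which the MMRM and ANCOVA of the same endpoint use: a modest, avoidable loss of precision

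*SAP*

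**What the plan says.** **Primary model (SAP 6.9.1.1).** "The Hierarchical Logistic Model will be used to model the dose response in HbA1c change from baseline to the 26-week endpoint". The week-26 change is normal around an arm mean θ_d with common variance σ². That mean is a function of dose strength plus a dose-specific deviation, and dulaglutide has its own independent mean. No patient-level covariate appears. Protocol 10.3.3.1 names none either.

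**Imputation.** "Any missing responses for the primary outcome will be imputed using the longitudinal integrated two-component prediction (ITP) model". The ITP model contains an arm mean, a patient effect, a residual and a time curve, again without baseline covariates. The titration form changes only the mean curve.

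**Decision quantities.** The stated aim is to "examine the probability each LY3298176 dose has demonstrated superiority relative to placebo", with a margin of −0.8%. The success rule is narrower: "The primary objective will be met if at least 1 of the 90% credible intervals" excludes that margin in favour of LY3298176.

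**Where the model is reused.**
- Non-inferiority to dulaglutide (SAP 6.9.1.2), met if the upper limit is "less than 0.3% (non-inferiority margin) for at least one LY3298176 dose arm".
- A supportive on-treatment analysis (SAP 6.9.1.3): "An analysis using the same statistical model as the primary analysis will also be performed".
- HbA1c at 12 weeks (SAP 6.9.2.1).
- Body weight, with a different dose-response curve (SAP 6.9.2.1): "Similar Bayesian dose-response analysis as for HbA1c will also be performed for the change in body weight".

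**Elsewhere in the plan.** SAP 5.2 stratifies randomisation by baseline HbA1c category, metformin use and BMI category. SAP 6.1.1 and 6.1.2 adjust the MMRM and ANCOVA for metformin use, BMI category and, for the primary endpoint, continuous baseline HbA1c.

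**The concern.** The plan treats these three factors as worth balancing at randomisation and worth adjusting for in every frequentist model of 26-week HbA1c, but omits them from the analysis it calls primary. No reason is given.

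Two consequences follow if the factors are prognostic. First, variance that baseline data could explain stays in σ², so credible intervals are wider than needed. Second, stratification already reduces the true sampling variation of the arm differences, and a model that ignores the strata takes no credit for this, so its intervals are conservative.

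What is at stake is precision, not validity. It bears most on the per-dose probabilities of beating placebo by 0.8%, in a study meant to support Phase 3 dose selection, and on the dulaglutide comparison. No planned analysis gives a covariate-adjusted probability of beating −0.8%.

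**Working it through.** **Inputs from the documents (SAP 5.3, 6.1, 6.9.1.1).** 300 randomised, 10% dropout, 45 completers per arm; SD 1.0%; mean changes 0 (placebo), −0.74, −1.17, −1.29 and −1.44 (1, 5, 10 and 15 mg) and −1.28 (dulaglutide); margin −0.8%; one-sided 90% interval (z = 1.2816).

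**Reproducing the plan's figure without covariates.**
- SE of a difference = 1.0 × √(2/45) = 0.2108; half-width = 1.2816 × 0.2108 = 0.270.
- Chance that one dose clears the margin = Φ((|effect| − 0.8)/0.2108 − 1.2816).
- 15 mg: Φ(0.64/0.2108 − 1.2816) = 96.0%. 10 mg: Φ(0.49/0.2108 − 1.2816) = 85.1%. 5 mg: Φ(0.37/0.2108 − 1.2816) = 68.2%.
- At least one of four doses against a shared placebo arm, simulated: 98.3%. With the SAP's own dose-response model and priors: 97.9%.

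The stated figure is about 98%, so it stands.

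**Effect of adjustment.** If the covariates explain a fraction R² of the variance of the 26-week change, the residual SD becomes 1.0 × √(1 − R²). The documents give no R², so 0–30% is assumed. At R² = 20%, for example, the SE is 0.2108 × 0.894 = 0.1886 and 10 mg gives Φ(0.49/0.1886 − 1.2816) = 90.6%.

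**Simulation with stratified randomisation.** Further assumptions: permuted blocks of 6 in 8 strata, a median HbA1c split, 70% on metformin, 50% with BMI ≥30. Least squares with and without the covariates; success if difference + 1.2816 × SE < −0.8; 12,000 trials per setting. Ranges cover R² coming all from HbA1c or shared equally among the three factors. Entries are unadjusted → adjusted; the last four columns are the chance (%) of clearing −0.8%.

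| R² | Half-width | 5 mg | 10 mg | 15 mg | At least one dose |
|---|---|---|---|---|---|
| 10% | 0.270 → 0.257 | 68.2–68.4 → 71.0 | 85.6–86.0 → 88.0 | 96.4–96.6 → 97.2 | 98.4 → 98.8 |
| 20% | 0.270 → 0.242 | 68.6–69.1 → 74.5 | 86.3–87.0 → 90.6 | 96.7–97.1 → 98.2 | 98.5–98.7 → 99.2 |
| 30% | 0.270 → 0.226 | 69.1–70.1 → 78.8 | 87.0–88.0 → 93.4 | 97.2–97.6 → 99.0 | 98.8–98.9 → 99.6 |

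- Intervals are 5, 11 and 16% narrower. At R² = 0 the adjusted SE is 0.1% wider, so adjustment costs almost nothing when it does not help.
- The unadjusted reported SE exceeds the true sampling SD by 3–4, 6–9 and 9–14%. Its nominal 90% interval covers 90.7–90.8, 91.4–91.8 and 92.0–92.9%. The adjusted SE is calibrated (ratio 0.999).
- Non-inferiority rule of SAP 6.9.1.2, read as a one-sided 90% limit, at least one dose (6,000 trials): 87.5–88 → 89–90%, 88 → 91–92%, 89 → 94%. The plan's figure of more than 95% is at 80% confidence and reproduces at 95.1%; the gap down to 88% comes from the confidence level, not from missing covariates.

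**Check against the SAP's own model.** Fitting the hierarchical logistic model with its priors by MCMC (200 trials per setting, complete data), the half-width falls from about 0.275 to 0.261, 0.247 and 0.232 at R² = 10, 20 and 30%, or 5, 10 and 16% narrower. A separate calculation with that model at multiple correlations of 0.3–0.5 (R² 9–25%) moves 10 mg from 84% to 87–91% and 5 mg from 66% to 69–75%. Levels are about 2 points lower than under least squares; the gains are similar.

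**The case against.** The strongest reply is that the pre-specified decision hardly changes. The at-least-one-dose rule is near its ceiling, there is no bias, and conservative intervals threaten no superiority claim. **This stands**, and it is why the point is minor.

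The larger gains belong to quantities with less formal weight. The SAP sets no per-dose success threshold, and Protocol 10.3.3.3.1 reserves the dulaglutide comparison for internal business decisions. This also stands, though per-dose probabilities are what SAP 6.9.1.1 sets out to examine and what a dose-finding study is read for.

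Adjusted evidence is already planned: MMRM and ANCOVA of the same endpoint (SAP 6.9.1.3), MMRM at the second interim (SAP 6.14.2) and PK/PD models of HbA1c (SAP 6.12). With weak priors, an approximate adjusted probability could be derived from the MMRM estimate and its SE. True, but nobody has specified doing so, and those models are set up to report means, 95% intervals and p-values. The loss is confined to the Bayesian probabilities and intervals.

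Software and timing may be obstacles. The SAP already made one concession "because of limitations in FACTS", and the documents do not say whether that program takes covariates. Protocol 10.3.1 permits it without requiring it. Changing the primary likelihood shortly before the primary lock could count as altering a principal feature and carries a credibility cost. That is a fair objection to the full change, but not to one added supportive analysis.

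Finally, the ITP patient effect already carries each patient's earlier post-baseline values into the imputation, so no efficiency loss is claimed there.

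**Conclusion.** The point holds as a low-severity, optional improvement. The primary Bayesian analysis omits covariates that the rest of the plan uses, without explanation. Over an assumed R² of 10–30%, adjustment would narrow its intervals by 5–16%. It would raise the chance of clearing −0.8% by about 3 to 10 points at 5 mg, 2 to 6 at 10 mg and under 2 at 15 mg, and by under 1 point for at least one dose.

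The size depends on R², block size and strata proportions, none of which the documents give, and on reading the 1.0% SD as the raw within-arm spread. That is the natural reading of σ in the primary model and it reproduces the 98%. If 1.0% were instead a covariate-adjusted SD, the unadjusted least-squares model would give roughly 95.4–97.7% for at least one dose over the same R² range, against 98.2% adjusted.

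**What to change.** **Full change.** Write the likelihood as y_T ~ N(θ_d + b₁(baseline HbA1c − mean) + b₂·metformin + b₃·BMI category, σ²), with all covariates centred and weak normal priors on the b's. Add the same terms to the ITP mean, including its titration form, so that imputation and analysis models agree. Keep the −0.8% rule on θ_d − θ_0 and the 0.3% rule against dulaglutide as they are. Check the common-slope assumption with the treatment-by-baseline HbA1c check that Protocol 10.3.3.2 already plans for the MMRM.

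**Minimum change.** If the primary must stay in FACTS and FACTS cannot take covariates, leave it untouched. Pre-specify the covariate-adjusted Bayesian model as one supportive analysis reporting the same −0.8% probabilities, and add a sentence saying why the primary has no covariates.

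**Cost.** No new data. The full change needs SAP wording, coding and validation of the joint MCMC (possibly outside FACTS), a common-slope assumption, and a judgement on whether a protocol amendment is required. The minimum change adds one analysis, with its own coding and validation.
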